## 5. ANALYSIS SETS

Individuals who do not meet the criteria for participation in this study (screen failure) may not be rescreened.

Analysis Population	Description
Enrolled	All subjects who sign the ICF
Safety Analysis Set (SAS)	All subjects assigned to study treatment and who took at least 1 dose of study treatment. Subjects will be analyzed according to the treatment they actually received.
Pharmacokinetic Analysis Set (PKAS)	All subjects assigned to study treatment, who took at least 1 dose of study treatment, and provided at least 1 PK sample. Subjects may be excluded from the PKAS on an individual basis, upon review of all records that have the potential to affect the PK data (e.g., dosing records, AEs, bleeding sampling records, concomitant medications other than aspirin/clopidogrel/apixaban/dabigatran, protocol deviations of diet restriction).

## 6. GENERAL ASPECTS OF THE STATISTICAL ANALYSIS

### 6.1. Key Definitions

The Study Day is the day relative to the first day of study drug administration (Day 1).

Unless otherwise specified, Baseline is the last non-missing observation before the administration of any study treatment.

### 6.2. Visit Windows and Time Points

There are no plans to derive visit windows, and visits will be used in the analyses as reported on the eCRF.

### 6.3. Multiplicity Issues

For this early phase study, no multiplicity adjustment will be necessary as no hypothesis testing is being done.

### 6.4. Subgroup Analyses

Although no subgroup analyses are planned, Part A results will be presented by treatment (LT3001 and placebo) and population (Chinese and Non-Asian) and Part B results will be presented by cohort.

### 6.5. Missing Data

For prior and concomitant medication summaries, if the medication start date is completely missing then the medication will be considered both prior *and* concomitant unless it can be determined that the medication end date occurred prior to any study drug administration. If the medication start date is partially missing and the partial date is not sufficient to determine if the medication was taken after study drug administration then the medication will be considered both prior *and* concomitant for the study unless the partial date is clearly after the date of first study drug administration (in which case it will be considered concomitant only) or the medication end date is prior to any study drug administration (in which case it is prior only).

Completely missing or partially missing adverse event onset dates will be imputed as follows in case due diligence to obtain accurate adverse event information fails:

- If the adverse event start date is completely missing then the adverse event will be considered treatment-emergent unless it can be determined that the adverse event end date occurred prior to administration of any study drug. If this is the case, the adverse event will not be considered treatment-emergent.
- If the adverse event start date is partially missing and the partial date is not sufficient to determine if the event occurred after the administration of any study drug, then the adverse event will be considered treatment-emergent unless it can be determined that the adverse event end date occurred prior to the start of the study.

No other missing data will be imputed.

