### 9.1.1. Time Period and Frequency for Collecting AE and SAE Information

All AEs and SAEs will be collected from the signing of the ICF until the follow-up visit at the time points specified in the SoA ([Section 2](#)).

Medical occurrences that begin before the start of study treatment but after obtaining informed consent will be recorded on the Medical History/Current Medical Conditions section of the case report form (CRF) not the AE section.

All SAEs will be recorded and reported to the sponsor or designee within 24 hours, as indicated in [Appendix 4](#). The Investigator will submit any updated SAE data to the sponsor within 24 hours of it being available.

Investigators are not obligated to actively seek AE or SAE in former study participants. However, if the Investigator learns of any SAE, including a death, at any time after a participant has been discharged from the study, and he/she considers the event to be reasonably related to the study treatment or study participation, the Investigator must promptly notify the sponsor.

The method of recording, evaluating, and assessing causality of AE and SAE and the procedures for completing and transmitting SAE reports are provided in Appendix 4.

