- **DEFINITELY:** This category applies to those AEs that the Investigator feels are incontrovertibly related to test drug/study procedure. An AE may be assigned an attribution of definitely related if or when it meets all of the following criteria: (1) it follows a reasonable temporal sequence from administration of the drug /study procedure; (2) it could not be reasonably explained by the known characteristics of the subject's clinical state, environmental or toxic factors, or other modes of therapy administered to the subject; (3) it disappears or decreases on cessation or reduction in dose and recurs with re-exposure to drug (if rechallenge occurs); and (4) it follows a known pattern of response to the test drug /study procedure.

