### 7.4. Prior and Concomitant Medication

Medications will be separated into prior and concomitant medications. Prior medications are those with start and stop date before the first date of any study drug administration. Concomitant medications are those with either start date prior to the date of first study drug administration and were ongoing while for the duration of the study or those with start date after the date of first study drug administration. A medication can be considered both prior and concomitant.

All medications will be coded according to the latest version of the WHO Drug Dictionary and listed by subject. Prior and concomitant medications will be flagged accordingly. Concomitant medication will be summarized using the anatomical/therapeutic/chemical (ATC) code classification of drugs based on the WHO dictionary.

All medications will be listed. Prior and concomitant medications will be flagged accordingly.

The concomitant medications taken during Part B as part of the study design (aspirin, clopidogrel, apixaban or dabigatran) will not be included in these analyses.

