### 9.1. Adverse Events

Adverse Events will be coded according to the latest version of the MedDRA dictionary. For this study, surveillance of adverse events (AE) will begin from Day 1 of the treatment period until the end of the follow-up or early termination.

Adverse events shall be recorded starting at signing of ICF. AEs will be defined as treatment-emergent adverse events (TEAE), if they occurred after administration of any study treatment or if they started prior to study drug administration but worsened after dosing, given that worsening started within the treatment period.

Only TEAEs shall be summarized in the clinical study report. An overall summary with number and percentage of subjects with all different TEAE categories, like treatment-related, serious, leading to withdrawal, and fatal will be provided. Incidence and severity of TEAEs will be summarized within System Organ Class (SOC), and within Preferred Term (PT).

TEAEs will be summarized by relationship per SOC and PT. Relationships will be categorized into related (includes “Related”, “Possibly Related” and “Probably Related”) and unrelated (includes “Not Related” and “Unlikely Related”).

TEAEs will also be summarized by maximal severity per SOC and PT. To count the number of subjects with any TEAEs, if a subject has multiple TEAEs coded to the same PT within the same SOC, the subject will be counted once under the maximal severity.

All AEs will be listed by subject. Serious AEs (SAEs), TEAEs, and AEs leading to withdrawal will be flagged accordingly.

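### Two SAP classification rules misplace records as written: the partial-onset-date rule for adverse events (if study start means consent or screening) and the definitions of prior and concomitant medication

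*SAP*

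**What the plan says.** **Adverse events with incomplete onset dates (SAP 6.5).** Two adjacent bullets apply. If the onset date is completely missing, the event is treatment-emergent "unless it can be determined that the adverse event end date occurred prior to administration of any study drug". If it is partly missing and the known part cannot settle whether onset followed dosing, the event is treatment-emergent "unless it can be determined that the adverse event end date occurred prior to the start of the study". The SAP does not define study start.

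**What a TEAE is (SAP 9.1).** Events qualify "if they occurred after administration of any study treatment or if they started prior to study drug administration but worsened after dosing". The same section says "Adverse events shall be recorded starting at signing of ICF". Protocol 9.1.1 also collects AEs from consent, but then sends certain records to the medical history page instead of the AE page: "Medical occurrences that begin before the start of study treatment but after obtaining informed consent".

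**Medications (SAP 7.4).** Prior means that both start and stop fall before the first study drug date. Concomitant covers drugs started before that date that "were ongoing while for the duration of the study or those with start date after the date of first study drug administration". The next sentence allows one medication to carry both labels. SAP 6.5 separately says that a drug with a missing or uninformative start date is both prior and concomitant, with exceptions such as an end date before study drug.

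**Causality.** Under "Relationships will be categorized into related", SAP 9.1 lists *Related*, *Possibly Related* and *Probably Related*, against *Not Related* and *Unlikely Related*. Protocol Appendix 4 uses UNRELATED, UNLIKELY, POSSIBLY, PROBABLY and DEFINITELY. Of the last it says: "This category applies to those AEs that the Investigator feels are incontrovertibly related to test drug/study procedure".

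**The concern.** An event known to have ended before the first dose can neither have started nor worsened after it. A date rule that calls it treatment-emergent therefore contradicts the TEAE definition it is meant to serve. The direction is also odd: knowing part of the onset date gives a worse classification than knowing none of it. Adverse events are a primary endpoint in both parts, and SAP 9.1 summarises only TEAEs, so this rule decides what enters the main safety tables.

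The medication definitions matter because the drugs that fall between them are those that overlap dosing for only part of the study. A summary of concomitant use in an interaction study should show exactly those. The case is foreseeable: protocol 7.11 permits acetaminophen at any time, so a first tablet on Day 1 would be in neither class.

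**Working it through.** No stated figure needs reproducing. The check is to apply the written rules to test records.

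**(a) TEAE date rule.** For an event with a known end date:

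- onset completely missing: TEAE unless end < first dose
- onset partial and uninformative: TEAE unless end < study start

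The two disagree when study start ≤ end < first dose. Screening runs from Day -30 to Day -1 (schedules of activities), which is 30 days. The table sweeps end dates over the 40 days before first dose, with consent on the first screening day. The 40 is only an illustration.

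| Rule | Pre-dose end dates classed as TEAE |
|---|---|
| Completely missing onset | 0 of 40 |
| Partial onset, study start = consent/screening | 30 of 40 |
| Partial onset, study start = Day 1 | 0 of 40 |
| Partial onset, after the fix | 0 of 40 |

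Thirty is the maximum, and it needs a partial date that is uninformative over the whole window. Take, for illustration, consent on 18 February and first dose on 20 March 2021. A year-only onset leaves every end date from 18 February to 19 March exposed (11 + 19 = 30). An onset known only as March 2021 leaves 1 to 19 March (19 days).

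**(b) Medication definitions.** Day 1 is the first-dose date.

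| Start | Stop | Class under SAP 7.4 | Class after the fix |
|---|---|---|---|
| Day -10 | Day -2 | prior | prior |
| Day -10 | Day 1 or Day 3 | neither | both |
| Day -10 | ongoing throughout | concomitant | both |
| Day 1 | any | neither | concomitant |
| Day 3 | any | concomitant | concomitant |

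No record can be both under SAP 7.4: prior requires a stop before first dose, and each concomitant branch requires use after it. SAP 6.5 gives a different answer for the same drug. If it stopped on Day 3 and its start date is missing, it is both; if its start is known to be Day -10, it is neither.

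**(c) Causality labels.** Matched literally, UNLIKELY, POSSIBLY and PROBABLY find a group. DEFINITELY and UNRELATED do not.

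**(d) Weight of one subject.** A Part B cohort has 12 subjects: 1/12 = 8.3 percentage points. The Part A LT3001 group has 12 if 3:1 applies to all 16 (16 × 3/4). It has 11 if the sentinels are split 2:2 and the other 12 are split 3:1 (2 + 9): 1/11 = 9.1 points.

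**The case against.** The strongest reply on the TEAE rule is that study start may mean Day 1. SAP 9.1 says AE surveillance begins on Day 1 of the treatment period, and SAP 6.1 counts study days from first dosing. On that reading nothing is misplaced. The screening reading remains the more natural one: protocol 5.1 includes screening in the roughly five weeks of required Part A procedures, and the neighbouring SAP bullet names study drug when it means dosing. The ambiguity is itself a reason to change the wording.

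The reply on frequency stands. The rule applies only after attempts to obtain the date have failed, and protocol 9.1.1 should move most of these events to medical history. That limits the route without closing it, since SAP 9.1 records AEs from consent.

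On medications, the garbled phrase could be a slip for *ongoing while on study*, and SAP 6.5 suggests that any overlap was meant to count. That is a fair guess at intent, but it would still leave a drug started on the first-dose date unclassified. Protocol 7.11 also restricts most medication, so few records are exposed.

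On causality, a reader might infer that DEFINITELY related events drop out of the related group. The documents do not show that. Both scales have five levels, and *Related* is the evident counterpart of DEFINITELY, as *Not Related* is of UNRELATED. The SAP's list is introduced by *includes*, which need not be exhaustive. It is a label mismatch with no demonstrated loss of events.

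**Conclusion.** Two rules are wrong as written, with limited reach.

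The partial-date bullet in SAP 6.5 misclassifies an event only if its partial onset date is uninformative about dosing, its end date is known, that end falls between study start and first dose, and study start means consent or screening. It is not true that every partly dated event ending before dosing becomes a TEAE. One that ended before study start, or whose partial date settles the timing, is handled correctly. The error can only over-count TEAEs. The number of affected records cannot be known from the documents and is probably small.

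The SAP 7.4 gap covers medications started before first dose and stopped during the dosing period, and those started on the first-dose date. A reader might extend it to any drug stopped during dosing, but one started after the first-dose date is concomitant. Nor does it drive PKAS exclusions, which SAP 5 bases on individual record review. All medications are listed, so only the flags and the ATC summary are affected.

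The 8.3 to 9.1 points is what one subject weighs, not an estimate of bias. It applies to any-TEAE incidence only if the misclassified event is that subject's sole TEAE, and it has no bearing on the medication rule. No hypothesis test or sample size is touched.

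**What to change.** - **SAP 6.5, second AE bullet:** replace *the start of the study* with *administration of any study drug*, matching the bullet above it.
- **SAP 7.4:** define prior as started before first study drug, and concomitant as taken on or after the first study drug date, whatever its start or stop date. Keep the statement that both flags are allowed. This also agrees with SAP 6.5.
- **SAP 9.1 (clarification only):** use the protocol's labels, with related = POSSIBLY, PROBABLY, DEFINITELY and unrelated = UNRELATED, UNLIKELY.

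The cost is three sentences in the SAP and the matching derivations, with no new data. Make the change before database lock, so that the handling is not left to programming judgement.

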## 7. DEMOGRAPHIC AND BASELINE CHARACTERISTICS

### 7.1. Subject Disposition and Populations

Summary tables for subject disposition will be presented for all enrolled subjects by Part and cohort. For Part A the disposition will be presented by treatment (LT3001 and placebo) and population (██████████), and for Part B the disposition will be presented by cohort. The subject disposition summary will contain the numbers of subjects who signed informed consent, failed screening, were randomized (Part A) or enrolled (Part B), completed that Part, and discontinued the study.

The primary reasons for premature discontinuation during the treatment periods will be summarized by Part and cohort for the SAS (Safety Analysis Set).

The number of subjects included in each analysis population will also be displayed.

Listings will also be presented on subject disposition and protocol violations.

### 7.2. Demographic and Baseline Characteristics

All subjects in the SAS will be used to summarize the demographic and baseline characteristics with respect to key variables such as age, sex, height, body weight, BMI, ethnicity and race. Summaries for other variables may be provided if needed.

Continuous variables will be summarized with descriptive statistics: n, mean, standard deviation, median, minimum, and maximum value. Categorical variables will be summarized with the number and percentages.

Other baseline characteristics such as COVID-19 screening, serum hcG pregnancy test, urine drug screen and alcohol breath test, and serology (HIV, HBV, HCV) screening will be listed for each subject.

A subject listing for demographic information will be provided by study part, cohort, and treatment (LT3001 or placebo).

### 7.3. Medical History

Medical history including existing diseases will be coded according to the latest version of the MedDRA dictionary. Frequency tables of the number and percentage of subjects by SOC (System Organ Class) and PT (Preferred Term) will be provided for the SAS.

Medical history will also be listed by subject.

### 7.4. Prior and Concomitant Medication

Medications will be separated into prior and concomitant medications. Prior medications are those with start and stop date before the first date of any study drug administration. Concomitant medications are those with either start date prior to the date of first study drug administration and were ongoing while for the duration of the study or those with start date after the date of first study drug administration. A medication can be considered both prior and concomitant.

All medications will be coded according to the latest version of the WHO Drug Dictionary and listed by subject. Prior and concomitant medications will be flagged accordingly. Concomitant medication will be summarized using the anatomical/therapeutic/chemical (ATC) code classification of drugs based on the WHO dictionary.

All medications will be listed. Prior and concomitant medications will be flagged accordingly.

The concomitant medications taken during Part B as part of the study design (aspirin, clopidogrel, apixaban or dabigatran) will not be included in these analyses.

## 7.5. Protocol Deviations

Protocol deviations and major protocol deviations are defined in the Clinical Monitoring Plan according to the ICH E3(R1) guidelines.

Protocol deviations are identified and recorded in the paper Protocol Deviation Log (PD Log) by the site staff. The clinical research associate (CRA) should review and ensure the deviations are accurately and completely recorded in the PD Log and signed by the investigator. Appropriate deviation category (i.e., major or minor) should be assigned as the table below.

Protocol Deviation Category	Major	Minor
Inclusion/Exclusion Criteria	X	
Informed Consent	X	
Enrollment: Enrolled but dosed incorrectly per cohort	X	
Randomization: Not randomized	X	
Investigation Product Dosing: Incorrect IP given to subject	X	
Investigation Product Dosing: IP dosing	X	
Out of Time Window Procedures		X
Study Procedure: Compliance		X
Study Procedure: Site Staff Authorization, Delegation, Training	X	
Blindness Failure	X	

All protocol deviations will be transferred from the completed PD log and finalized before the database lock.

Protocol deviations will be listed by subject.

## 8. PHARMACOKINETIC ANALYSIS

For PK analysis of LT3001 and concomitant medications (aspirin, clopidogrel, apixaban or dabigatran) blood samples will be collected throughout the treatment periods according to the PK sampling schedule in the Schedule of Activities (SoA) of the protocol and this SAP. All PK analysis will be based on the PKAS.

### 8.1. Handling of BLQ Values

To compute summary statistics for plasma concentration the BLQ plasma concentrations will be set to 0 for except for calculating geometric means and geometric CV%. For these two summary statistics it is set to LLOQ/2.

The BLQ values will be set to 0 in concentration-by-time linear plots and will be set to LLOQ/2 in concentration-by-time semi-logarithmic plots for mean and individual plots.

For calculation of the PK parameters, BLQ value(s) that occur at the beginning or at the end of serial sampling (before the first or after the last quantifiable concentration value, respectively) will be treated as zero. A BLQ value that is embedded between two quantifiable points will be treated as missing data. If consecutive BLQ concentrations are followed by quantifiable concentrations in the terminal portion of the concentration curve, these quantifiable values may be excluded from the pharmacokinetic analysis by assigning them a value of missing unless otherwise warranted by the concentration-time profile.

### 8.2. Plasma PK: Part A

#### Plasma PK Concentration

Plasma concentrations of LT3001 will be summarized by population (Chinese vs. Non-Asian) with descriptive statistics: n, mean, SD, CV%, geometric mean, geometric CV%, median, minimum, and maximum.

Plots of mean (SD) plasma concentration by time will be presented for LT3001 in linear and semi-logarithmic scales as well.

Plasma concentrations of LT3001 (Part A) at each nominal timepoint will be listed by subject.

#### Plasma PK Parameters

The following plasma PK parameters will be calculated for Part A for LT3001:

- $C_{\max}$ : Maximum (peak) plasma drug concentration during a dosing interval
- $C_{\min}$ : Trough plasma concentration
- $C_{av}$ : Mean steady-state drug concentration
- $t_{\max}$ : Time to reach the observed maximum (peak) plasma concentration

- $\lambda_z$ : Apparent first-order terminal elimination rate constant, calculated by linear least-squares regression analysis on the terminal log-linear phase of the plasma concentration vs time curves using at least 3 timepoints
- $AUC_{0-\infty}$ : Area under the plasma concentration-time curve from time zero to infinity, calculated as  $AUC_{0-t} + C_t / \lambda_z$ , where  $C_t$  is the last measurable concentration
- $AUC_{0-t}$ : Area under the plasma concentration-time curve from time zero to the time of last quantifiable concentration, calculated by the linear trapezoidal linear interpolation method
- $AUC_{0-\tau}$ : Area under the plasma concentration-time curve over the dosing interval  $\tau$  at steady-state
- $R_{acc}$ : Accumulation ratio calculated as  $AUC_{0-\tau, 1st\ dose}/AUC_{0-\tau, last\ dose}$  for the multi-day LT3001 regimens
- $MRT_{0-\infty}$ : Mean residence time, calculated as  $[AUMC_{0-\tau} + \tau(AUC_{0-\infty} - AUC_{0-\tau})]/AUC_{0-\tau} - (TI/2)$  where  $AUMC_{0-\tau}$  is the area under the moment curve over dosing interval  $\tau$  and  $TI$  represents infusion duration
- $t_{1/2, \lambda}$ : Elimination half-life, calculated as  $0.693 / \lambda_z$
- $CL$ : Total body clearance of the drug from plasma, calculated as  $Dose / AUC_{0-\infty}$
- $V_z$ : Apparent volume of distribution during the terminal phase, calculated as  $(Dose / AUC_{0-\infty}) / \lambda_z$
- $V_{ss}$ : Apparent volume of distribution during steady state, calculated as  $CL \times MRT$

All calculations for plasma PK parameters will be based on actual dosing and sampling times recorded during the study. Plasma and urine pharmacokinetic parameters will be summarized (n, arithmetic mean, SD, CV%, minimum, median, and maximum) and listed by subject. Geometric mean (GM) and geometric CV% will also be presented for all AUC,  $C_{max}$ ,  $C_{av}$ , and  $C_{min}$ .

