## **9.2. Treatment of Overdose**

The dose level of LT3001 drug product will be calculated by the Investigator or a qualified designee based on the study subject's body weight. Since drug accumulation is not anticipated due to the short half-life of LT3001 and subjects will only receive LT3001 drug product administered by an Investigator or a qualified designee and under close monitoring, it is anticipated that the risk of overdose or medication error will be low.

An overdose is any dose of study treatment given to a subject or taken by a subject that exceeds the dose described in the protocol. Any overdose, with or without associated AEs, must be promptly reported to the Medical Monitor. Overdoses without signs or symptoms do not need to be recorded as AEs; in case of any AEs associated with the overdose, these should be reported on relevant AE/SAE sections in the eCRF.

Overdoses and medication errors will be documented as protocol deviations and communicated to the project manager.

No specific therapy for overdose of LT3001 drug product exists. In the event of overdose or medication error, appropriate therapy for the patient's symptoms and clinical status should be provided.

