$V_{ss}$	Apparent volume of distribution during steady state, calculated as $CL \times MRT$
$Ae_{x-y}$	Amount of drug excreted in urine within a collection interval (x to y hours), where the values of x to y are 0 to 12 and 12 to 24
$Ae_{0-24}$	Total amount of drug excreted in urine over the entire collection period (0 to 24 hours)
$Fe_{0-24}$	Fraction excreted in urine from 0 to 24 hours after dosing, calculated as $Ae_{0-24} / Dose \times 100$
$CL_r$	Renal clearance, calculated as $Ae_{0-24} / AUC_{0-\infty}$
$Racc$	Accumulation ratio calculated as $AUC_{0-t, 1st\ dose} / AUC_{0-t, last\ dose}$ for the multi-day LT3001 regimens.

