#### **10.3.2. Pharmacokinetic Analyses**

All PK analyses will be performed on the Pharmacokinetic Analysis Set. The PK parameters will be calculated, as appropriate, using a non-compartmental approach.

Plasma concentrations will be summarized by cohort over each scheduled sampling time using descriptive statistics. Individual plasma concentration data versus actual time points will be presented in listings. Pharmacokinetic parameters will be summarized by dose using descriptive statistics. Individual PK parameters will be presented in a data listing.

The effect of aspirin, clopidogrel, apixaban or dabigatran on the PK of LT3001, as well as the effect of LT3001 on the PK of aspirin, clopidogrel, apixaban or dabigatran, will be assessed by comparing PK parameters of LT3001 and these concomitant medications. A linear mixed-effects model with fixed factors for Cohort and Day (day of with/without concomitant drug use), and subject as random effect on log PK-parameter will be used to calculate 90% confidence intervals for the geometric mean ratio of the  $AUC_{0-t}$ ,  $AUC_{0-\infty}$ ,  $AUC_{0-\tau}$  and  $C_{max}$ . Differences between treatments when LT3001 drug product was administered alone or with aspirin, clopidogrel, apixaban or dabigatran will be calculated for LT3001, aspirin, clopidogrel, apixaban, and dabigatran using ratios of geometric least squares mean and 90% confidence intervals (CI). The criteria of 90% CI within 50-200% of weak-effect boundaries will be firstly used for assessment. Only when the first criteria are satisfied, the second criteria of 90% CI within 80-125% of no-effect boundaries will be used for further assessment.

To investigate whether the dose of LT3001 drug product is accumulated in the 3-day TID regimen, the potential dose accumulation effect will be assessed by comparing PK parameters of the first dose and

the last dose in the multi-day TID regimen of LT3001 drug product. The comparisons will be conducted for occasions when LT3001 is alone or is coadministered with aspirin, clopidogrel, apixaban, or dabigatran. PK parameters for comparison include  $AUC_{0-t}$  and  $C_{max}$ .

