### Accumulation Ratio

To investigate whether the dose of LT3001 drug product is accumulated in the 3-day TID regimen, the potential dose accumulation effect will be assessed by comparing PK parameters of the first dose and the last dose in the multi-day TID regimen of LT3001 drug product.

Using a linear mixed-effects model with Race, Day (Day 1, first dose and Day 3, last dose), and Race-by-Day interaction as fixed effects, and subject as a random effect on log-transformed data, the geometric means and corresponding 95% CIs for  $AUC_{0-t}$ ,  $AUC_{0-\tau}$ , and  $C_{max}$  will be presented for Chinese and Non-Asian subjects by exponentiating the model-based least-squared means. The geometric mean ratios (last dose/first dose) and the corresponding 90% CIs will also be calculated overall and for each race based on this model to assess accumulation.

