### **Accumulation Ratio**

To investigate whether the dose of LT3001 drug product is accumulated in the multiday regimen, the potential dose accumulation effect will be assessed by comparing PK parameters of the first dose and the last dose in the multi-day TID regimen of LT3001 drug product. The comparisons will be conducted for occasions when LT3001 is alone or is coadministered with aspirin, clopidogrel, apixaban, or dabigatran.

For each cohort based on a linear mixed-effects model with Day (Day of first dose and Day of last dose) as a fixed effect, and subject as a random effect on log-transformed data, the geometric means and corresponding 95% CIs for  $AUC_{0-t}$ ,  $AUC_{0-\tau}$ ,  $C_{max}$ , and  $C_{trough}$  will be presented by exponentiating the model-based least-squared means. The geometric mean ratios (last dose/first dose) and the corresponding 90% CIs will also be calculated for each cohort based on this model to assess accumulation.

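### The accumulation ratio Racc is defined as first dose over last dose, the reciprocal of the last/first ratio that the SAP uses to assess accumulation

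*SAP*

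**What the plan says.** Racc is defined three times, each time as first over last.

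- Protocol section 9.4: "Accumulation ratio calculated as $AUC_{0-t, 1st\ dose} / AUC_{0-t, last\ dose}$ for the multi-day LT3001 regimens".
- SAP section 8.2 (Part A), Plasma PK Parameters: "Accumulation ratio calculated as $AUC_{0-\tau, 1st\ dose}/AUC_{0-\tau, last\ dose}$ for the multi-day LT3001 regimens".
- SAP section 8.3 (Part B), Plasma PK Parameters: the same ratio again, "AUC_{0-\tau, 1st\ dose}/AUC_{0-\tau, last\ dose".

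The SAP also has an Accumulation Ratio subsection for each part, based on a mixed model on log-transformed parameters. For Part A: "The geometric mean ratios (last dose/first dose) and the corresponding 90% CIs will also be calculated overall and for each race". For Part B: "The geometric mean ratios (last dose/first dose) and the corresponding 90% CIs will also be calculated for each cohort". The parameters analysed include the AUC on which Racc is built; for Part A the list reads "AUC_{0-t}$ , $AUC_{0-\tau}$ , and $C_{max}$ will be presented for Chinese and Non-Asian subjects", and Part B adds Ctrough.

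Protocol section 10.3.2 says only that "the potential dose accumulation effect will be assessed by comparing PK parameters of the first dose and" the last dose, and gives no direction for a ratio. Protocol section 9.2 states that "drug accumulation is not anticipated due to the short half-life of LT3001".

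**The concern.** An accumulation ratio should exceed 1 when exposure builds up over repeated dosing. As written, Racc does the opposite: accumulation gives a value below 1, and a fall in exposure gives a value above 1. A reader who takes Racc in its usual sense would draw the reverse conclusion from the table.

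The SAP also contradicts itself. The listed parameter and the model-based ratio answer the same question, in the same subjects, on the same AUC, but in opposite directions.

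The plasma PK parameters of LT3001 are a primary endpoint of both parts, Racc is one of the listed parameters, and both parts have an analysis devoted to accumulation. Every Part A and Part B listing and summary of Racc would carry the inversion.

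A smaller mismatch sits on the same line: the protocol builds Racc on AUC0-t and the SAP on AUC0-tau. AUC0-t stops at the last quantifiable concentration, which can fall at different times after the first and last doses, so the two are not the same quantity.

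**Working it through.** The documents state no numerical accumulation value, so there is no figure to reproduce. The check is of direction, then size, then whether the error can be undone afterwards.

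**Step 1: direction.** Let R = AUC(last)/AUC(first), the ratio in the SAP's Accumulation Ratio subsections. Racc as written is AUC(first)/AUC(last) = 1/R. When every subject has both doses measured, the geometric mean of Racc is exactly the reciprocal of the model's ratio on the same AUC, within a Part B cohort or within a Part A race group.

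**Step 2: size for a given change in exposure** (illustrative values of R; none comes from the documents).

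| R (last/first, SAP model) | Racc as written (1/R) |
|---|---|
| 0.80 | 1.25 |
| 1.00 | 1.00 |
| 1.10 | 0.909 |
| 1.25 | 0.800 |
| 1.30 | 0.77 |
| 1.50 | 0.667 |
| 2.00 | 0.500 |

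**Step 3: what the dosing schedule could produce.** Inputs from the documents: 15-minute infusions, three a day 3 hours apart, on three days, so the ninth dose starts 54 h after the first and tau = 3 h. The LT3001 half-life is not given in the visible text, so it is assumed over a range of 0.25 to 6 h. One-compartment kinetics with superposition are also assumed. With k = ln 2 / half-life, T = 0.25 h and B = (e^(kT) − 1)/(kT):

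R = 1 + B(1 − e^(−3k)) × Σ e^(−ka) / (1 − B e^(−3k)), summed over the times a from each earlier dose to the ninth: 3, 6, 24, 27, 30, 48, 51 and 54 h.

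Worked for a half-life of 1 h: k = 0.6931, B = 1.0919, e^(−3k) = 0.125. The denominator is 1 − 1.0919 × 0.125 = 0.8635. The doses 3 h and 6 h earlier contribute 1.0919 × 0.875 × (0.125 + 0.015625) = 0.1344, and the rest are negligible. So R = 1 + 0.1344/0.8635 = 1.156, and Racc as written = 0.865.

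| Assumed half-life (h) | R (last/first) | Racc as written |
|---|---|---|
| 0.25 | 1.0004 | 0.9996 |
| 0.5 | 1.019 | 0.981 |
| 1 | 1.156 | 0.865 |
| 2 | 1.513 | 0.661 |
| 3 | 1.803 | 0.555 |
| 6 | 2.424 | 0.413 |

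**Step 4: can the table be inverted later?** SAP 8.2 and 8.3 summarize PK parameters by n, arithmetic mean, SD, CV%, minimum, median and maximum. Geometric mean and geometric CV% are added for the AUCs, Cmax, Cav and Cmin, but not for Racc. Suppose R is lognormal with geometric mean 1.25 and log-SD 0.25 (both assumed). Then:

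- mean of last/first = 1.25 × exp(0.25²/2) = 1.25 × 1.0317 = 1.29
- mean of first/last = 0.80 × 1.0317 = 0.83
- reciprocal of the unrounded mean of first/last (0.8254) = 1.21, not 1.29

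The mean, SD and CV% would have to be recalculated from subject-level values.

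**The case against.** The case for treating this lightly is a fair one. The analysis that the SAP designates to assess accumulation is the mixed model, which is correctly oriented, covers AUC0-t, AUC0-tau and Cmax, and carries the only confidence intervals. Racc is descriptive and has no decision rule. Parameters are listed by subject, so each individual Racc can be inverted. The protocol expects no accumulation, and at assumed half-lives of 0.25 or 0.5 h Racc as written is 0.9996 or 0.981, hardly different from 1. The protocol does not contradict itself either, since its analysis section states no direction. The AUC0-t/AUC0-tau difference is covered by the statement in SAP section 2 that its methods take precedence over the protocol's.

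Most of this stands as a limit on consequence. The formal inference survives, the explicit contradiction lies inside the SAP, and the large discrepancies depend on half-lives that the visible text does not support. The expectation of no accumulation is a prior judgement that does not depend on this study's Racc. But none of it makes the formula right. The precedence statement works the other way on direction: it makes the inverted SAP formula the one to be programmed. Nor does access to individual values rescue the summaries (Step 4).

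One further point concerns the remedy. The SAP describes AUC0-tau as a steady-state quantity, which does not fit a first dose. The legible Cohort 2 schedule in the SAP samples LT3001 to 60±5 minutes after the start of infusion, against a 3-hour interval. Other sampling schedules are redacted or garbled, so this cannot be extended to every cohort. It bears on how AUC0-tau is obtained, not on which dose belongs in the numerator.

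**Conclusion.** The concern holds. Racc is inverted in Protocol 9.4 and in SAP 8.2 and 8.3, and in the SAP it is the reciprocal of the last/first ratio reported for the same purpose. The direction error is algebraic and rests on no assumption. Its size depends on the true accumulation: negligible if there is none, 0.77 against 1.30 for a 30% rise, 0.50 against 2.00 for a doubling. Those rises, the half-life range and the lognormal example are illustrations, not figures from the plan.

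The model-based ratios and their 90% CIs need no change. The Racc listings and summaries for both parts would be wrong as specified and could not be put right by inverting the reported means, so the formula should be corrected before analysis.

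**What to change.** Define Racc = AUC0-tau(last dose) / AUC0-tau(first dose of the same multi-day TID regimen) in Protocol 9.4 and in SAP 8.2 and 8.3. Naming the regimen matters in Part B, where the single Day 1 infusion could otherwise be taken for the first dose. Using AUC0-tau throughout removes the protocol/SAP mismatch and keeps Racc comparable with the model.

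In the same edit:

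- State that AUC0-tau for the first dose means AUC over the 3-hour interval after that dose, and say how it is obtained where sampling ends earlier.
- Add Racc to the parameters summarized by geometric mean and geometric CV%, so that the descriptive and model-based ratios can be compared directly.

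The cost is one formula line in three places, with no change to design, data collection or sample size. The two SAP lines control the analysis and should be corrected before programming. The protocol line goes through the amendment process in Appendix 3 and can be carried with the next amendment.
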